The sponsor, in conjunction with the DESC, will determine the RP2D of ASP0739 as a single agent and in combination with pembrolizumab, taking into consideration the safety and efficacy data, as well as other available data, such as pharmacokinetics and pharmacodynamics of ASP0739.

The dose level determined to be the RP2D must have data from at least 6 participants.

Dose Escalation Safety Committee:

A DESC consisting of sponsor representatives and investigators will convene once a dose level cohort completes the DLT observation period and data are available for review for the phase 1 dose escalation and safety lead-in. Additional details regarding responsibilities, membership requirements and safety review time points are included in the DESC Charter. The DESC will also review the aggregate safety data from the phase 1 dose escalation expansion and phase 2 expansion cohorts for single agent and combination therapy with pembrolizumab.

While safety data from the DLT observation period in the escalation cohorts are the minimum safety data needed for the DESC meeting, all available safety findings will be

considered by the DESC. The DESC will assess whether a longer DLT observation period is warranted based on emerging data. Additionally, only when determining the RP2D, the DESC may choose a more conservative dosing decision than the MTD selected by BOIN design, based on evaluation of the safety data and other available data.

The decision on the dose level for the next cohort will be based on the BOIN design. In addition, MTD will be determined by BOIN from at least 6 participants. The RP2D dose for expansion will not be higher than the MTD. If the RP2D is selected at the same dose level as the MTD based on the phase 1 dose escalation portion, the combination safety lead-in will start at one dose level lower than the MTD.

Phase 2 Single Agent

Once RP2D is determined, the phase 2 single agent cohorts may be opened in R/R SS, MRCL, ovarian cancer and other solid tumors known to express NY-ESO-1 (melanoma, NSCLC-adenocarcinoma and squamous cell and ESCC). If a confirmed response (partial response based on iRECIST [iPR] or complete response based on iRECIST [iCR], per independent central review or local assessment) occurs in other solid tumors known to express NY-ESO-1, a tumor-specific dose expansion cohort may be opened in that tumor type.

Objective response rate per iRECIST (iORR), as confirmed per independent central review, is monitored using the Bayesian optimal phase 2 (BOP2) design [Zhou et al, 2017]. For R/R SS, MRCL and ovarian cancer, initially 18 participants will be enrolled in each tumor-specific expansion cohort (stage 1). If the iORR does not meet the optimal stopping boundaries (see table below), then an additional 25 participants (stage 2) may be enrolled for a total maximum sample size of 43 participants. When the total number of participants reaches the maximum sample size of 43, it may be predicted that ASP0739 is effective if the number of responses is greater than or equal to 8.

Optimized Stopping Boundaries for SS, MRCL and Ovarian Cancer	
Number of participants treated	Stop if number of responses ≤
18	2

MRCL: myxoid/round cell liposarcoma; SS: synovial sarcoma

For the melanoma/NSCLC/ESCC cohort, after a minimum of 10 participants per tumor type are enrolled, if less than approximately 6 participants for each tumor type of melanoma, NSCLC-adenocarcinoma or squamous cell carcinoma or ESCC are NY-ESO-1 positive upon analysis of the most recent tissue sample, then additional participants may be enrolled into the tumor type with less than approximately 6 NY-ESO-1 positive participants.

UNIQUE to Japan Sites:

Japanese participants will only be enrolled into the monotherapy arm of the dose expansion cohort.

Phase 2 Single Agent Dose Expansion Cohort with Japanese Safety Lead-in

After the phase 1 dose escalation cohort has been completed, the phase 2 single agent dose expansion cohort with Japanese safety lead-in will be opened. The Japanese safety lead-in will enroll 3 to 8 safety evaluable participants to confirm Japanese tolerability of the RP2D of ASP0739. Japanese participants must be managed under hospitalization for 7 days from C1D1 through C1D8 during the Japanese safety lead-in. Prior to hospital discharge, the investigator must ensure participant safety by performing medical tests and procedures listed on Day 8 of Cycle 1. During the Japanese safety lead-in, an interval of 7 days will separate study treatment initiation for the second participant from the first participant. In the absence of toxicity, additional participants may be treated without any formal stagger.

The tolerability of ASP0739 single agent therapy RP2D will be assessed during the DLT observation period, which is from C1D1 to C1D28. Quantitative assessment of DLTs will be performed referring to the concept of a BOPIN design with the target DLT rate of 30% and optimal interval of (0.236, 0.359) to determine if the ASP0739 single agent therapy RP2D is tolerable and is based on a DLT occurrence after 28 days. The tolerability evaluation rule is as follows:

	Number of Participants evaluable for DLT Assessment					
	3	4	5	6	7	8
[Tolerable] If the number of participants with DLTs is equal or less than the number given in the corresponding cell, the ASP0739 single agent therapy RP2D can be determined to be tolerable.	0	0	1	1	1	1
[Stay] If the number of participants with DLTs is equal to the number given in the corresponding cell, enrollment is continued until the maximum number of participants is reached.	1	1	NA	2*	2*	2*
[Not tolerable] If the number of participants with DLTs is equal or greater than the number given in the corresponding cell, the ASP0739 single agent therapy RP2D is determined to be intolerable.	2	2	2	3	3	3

DLT: dose limiting toxicity; NA: not applicable; RP2D: recommended phase 2 dose; TEM: tolerability evaluation meeting

*When the number of participants for DLT assessment reaches the maximum number of participants and the recommended action is Stay, the tolerability of the dose will be assessed comprehensively at the TEM.

A minimum of 3 evaluable participants must be enrolled at the dose level used to determine the tolerability of RP2D in Japanese participants. Three to four safety evaluable participants are enrolled as initial assessment. If the evaluation is to be continued based on DLT

occurrence, additional 3 to 4 safety evaluable participants are enrolled. After the tolerability of RP2D is confirmed in Japanese participants, additional Japanese participants will be enrolled into dose expansion part continuously.

Tolerability Evaluation Meeting

A TEM consisting of sponsor representatives and investigators will convene once the number of Japanese participants [Section 10.1.5.1 Tolerability Evaluation Meeting] completes the DLT observation period and data are available for review. TEM members should consider all available safety findings when making their evaluations and decisions. Additional details regarding responsibilities, membership requirements and safety review time points are included in the TEM Charter.

Replacement of Participants in Japanese Safety Lead-in

Participants may be replaced in the safety lead-in if:

- The participant is discovered to have enrolled without fully satisfying the eligibility criteria.
- The participant received less than the planned dose in C1 for reasons other than a DLT.
- The participant has experienced no DLT and withdraws from the study before the end of DLT evaluation period.

The decision regarding replacement of individual participants will be made by the sponsor with discussions with the treating investigator. Participants who experience DLTs in the safety lead-in will not be replaced.

The participants experiencing a DLT will be discontinued from the study unless the participants are deriving clinical benefit from the study treatment in the opinion of the investigator; in those cases, after discussion with the sponsor, participants may be allowed to continue study treatment with ASP0739 upon resolution of the DLT event to \leq grade 1 or baseline.

A participant who meets the stopping criteria will not receive study drug at C2. Additionally, at the TEM, the aggregate safety data are reviewed if any study stopping rules below have been met:

- If a study participant develops a grade 4 DLT after receiving C1
- If a study participant develops a grade \geq 3 non-hematological AE that does not resolve to \leq grade 2 within 72 hours of onset
- Note: This event should be considered a DLT.
- If there is a delay in administration of C2 by $>$ 4 weeks, it may result in discontinuation of treatment after discussion with the sponsor.

Study enrollment and study treatment of the Japanese safety lead-in will be temporarily interrupted if any of the following events occur in a participant:

- Any death that is not related to disease progression occurring within 30 days of receiving ASP0739

- Occurrence of 2 grade \geq 4 DLTs in 2 participants
- Any grade 4 hypersensitivity reaction/anaphylaxis

Phase 2 Combination of ASP0739 + Pembrolizumab

Once safety lead-in is completed and 2 radiographic responses (iCR or iPR) are observed in the phase 2 dose expansion monotherapy cohort by local or central review, the phase 2 combination cohorts may be opened in the respective tumor type where the responses were observed.

For R/R SS, initially 22 participants will be enrolled in an expansion cohort (stage 1). If the iORR does not meet the optimal stopping boundaries (see table below) for R/R SS, then an additional 38 participants (stage 2) may be enrolled for a total maximum sample size of 60. When the total number of participants reaches the maximum sample size of 60, it may be predicted that ASP0739 in combination with pembrolizumab is effective if the number of responses is greater than or equal to 18.

Optimized Stopping Boundaries for SS	
Number of participants treated	Stop if number of responses \leq
22	3

SS: synovial sarcoma

For R/R MRCL, initially, 22 participants will be enrolled in an expansion cohort (stage 1). If the iORR does not meet the optimal stopping boundaries (see table below) for R/R MRCL, then an additional 38 participants (stage 2) may be enrolled for a total maximum sample size of 60. When the total number of participants reaches the maximum sample size of 60, it may be predicted that ASP0739 in combination with pembrolizumab is effective if the number of responses is greater than or equal to 18.

Optimized Stopping Boundaries for MRCL	
Number of participants treated	Stop if number of responses \leq
22	3

MRCL: myxoid/round cell liposarcoma

For R/R ovarian cancer, initially, 10 participants will be enrolled in an expansion cohort (stage 1). If the iORR does not meet the optimal stopping boundaries (see table below) for R/R ovarian cancer, then an additional 19 participants (stage 2) may be enrolled for a total maximum sample size of 29. When the total number of participants reaches the maximum sample size of 29, it may be predicted that ASP0739 in combination with pembrolizumab is effective if the number of responses is greater than or equal to 4.

Optimized Stopping Boundaries for Ovarian Cancer	
Number of participants treated	Stop if number of responses \leq
10	0

If both single agent and combination therapy expansion cohorts are open for the same tumor type, participants will be randomized to either single agent or combination therapy cohorts

and the randomization ratio will be based on the number of open slots still available at each cohort.

Replacement of Participants in Phase 2 Dose Expansion

If a participant in phase 2 is not response evaluable (defined as the response analysis set [RAS]), then an additional participant may be enrolled in that cohort based on sponsor discretion.

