- Grade 3 nausea and/or vomiting if not requiring tube feeding or total parenteral nutrition, or diarrhea and/or constipation if not requiring or prolonging hospitalization that can be managed to grade \leq 2 within 72 hours of onset with standard antiemetic or antidiarrheal medications used at prescribed dose
- Grade 3 liver function test (LFT) elevations that resolve to \leq grade 1 within 7 days; LFT elevations lasting $>$ 7 days that are considered to be clinically significant and at least possibly related to ASP0739 will be considered to be a DLT
- Grade 3 or lower irAEs that resolve to \leq grade 1 within 72 hours of onset after starting treatment including corticosteroids

Participants who are tolerating IP at a dose level that is being reviewed due to the occurrence of DLTs in another participant will not be automatically precluded from continued dosing during the safety review, and will be allowed to continue dosing for as long as tolerated unless directed otherwise as a result of the safety review by the DESC.

DLTs Requiring Discontinuation of Treatment

- If a study participant develops a grade 4 DLT after receiving cycle 1, then the study participant should be discontinued from treatment.
- If a study participant develops a grade \geq 3 non-hematological AE that does not resolve to \leq grade 2 within 72 hours of onset, it should be considered a DLT and the study participant should be discontinued from treatment.
- If there is a delay in administration of the second cycle by $>$ 4 weeks, it would result in discontinuation from treatment after discussion with the sponsor.

ASP0739 in Combination with Pembrolizumab Safety Lead-in

Enrollment in the combination therapy safety lead-in will start once phase 1 single agent dose escalation is completed and the RP2D is defined.

The combination therapy safety lead-in portion will evaluate the RP2D of ASP0739 with a fixed dose of 400 mg pembrolizumab in 6 to 9 participants with at least 6 DLT-evaluable participants. If the RP2D is selected at the same dose level as the MTD based on the phase 1 dose escalation portion, the combination safety lead-in will start at one dose level lower than the MTD.

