Safety lead-in will be guided according to the BOPIN design [Liu & Yuan, 2015] to determine if the RP2D of ASP0739 with a fixed dose of 400 mg pembrolizumab is tolerable and based on DLT occurrence after 28 days. After the planned number of evaluable participants has completed the DLT observation period of 28 days for a given dose level, safety for that dose level will be assessed. Safety lead-in will enroll 3 to 4 evaluable participants for the initial assessment of RP2D. A minimum of 6 participants must be enrolled at the dose level used to determine the RP2D. Enrollment will be staggered such that there will be a minimum of 28 calendar days between the treatment initiation of the first and second participants, as well as 14 calendar days between the second and third participants at the same dose level for the safety lead-in cohort. In the absence of toxicity, additional participants may be treated at a dose level without any formal stagger. An interval of 28 calendar days will separate study treatment initiation of the last patient in a dose cohort from the first participant treatment in sequential dose cohort.

Action	Number of Participants Treated at Current Dose Level					
	3	4	5	6	7	8
Escalate dose if number of participants with DLT \leq	0	0	1	1	1	1
Stay at current dose level if number of participants with DLT =	1	1	NA	2	2	2
De-escalate if number of participants with DLT = ^a	2	2	2 or 3	3	3 or 4	3 or 4
Stop if number of participants with DLT \geq	3	3	4	4	5	5

DLT: dose limiting toxicity; NA: not applicable

a. Dose de-escalation will be implemented as a single dose level reduction to a lower dose of ASP0739 (either from 1×10^8 to 1×10^7 or from 1×10^7 to 1×10^6) in combination with pembrolizumab 400 mg.

Definition of DLTs for ASP0739 and Pembrolizumab Combination Therapy

A DLT is defined as any of the following events that occur within 28 days starting with the first dose on C1D1 in the safety lead-in cohort and that is considered to be possibly, probably or definitely related to ASP0739 and/or pembrolizumab. Confirmation of DLTs will be made by the DESC. The severity of AEs will be assessed according to NCI-CTCAE, v5.0.

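### The combination lead-in table reuses the phase 1 Escalate row with no ceiling at the single-agent RP2D and no outcome that means tolerable

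*Protocol*

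**What the plan says.** Protocol 4.1 gives the purpose of the combination lead-in as "to determine if the RP2D of ASP0739 with a fixed dose of 400 mg pembrolizumab is tolerable", enrolling "in 6 to 9 participants with at least 6 DLT-evaluable participants". Section 4.2 likewise describes the combination as given at the single-agent RP2D. The first assessment uses 3 to 4 evaluable participants, and "A minimum of 6 participants must be enrolled at the dose level used to determine the RP2D". If RP2D and MTD are the same dose, "the combination safety lead-in will start at one dose level lower than the MTD".

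The lead-in table has the same four actions and counts as the phase 1 table. The row "Escalate dose if number of participants with DLT" carries the limits 0, 0, 1, 1, 1, 1 for 3 to 8 participants. Its single footnote says how to step down. The committee text in 4.1 adds "The decision on the dose level for the next cohort will be based on the BOIN design". It allows the DESC to be more conservative than BOIN only when determining the RP2D, and it caps only the expansion dose at the MTD.

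The Japanese single-agent lead-in, also in 4.1, confirms an RP2D at the same Escalate and Stay counts. There the row is reworded so that "the ASP0739 single agent therapy RP2D can be determined to be tolerable", and if the action is still Stay at maximum size, "the tolerability of the dose will be assessed comprehensively at the TEM".

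**The concern.** A lead-in that confirms a dose needs three outcomes at that dose: tolerable, not tolerable, or unresolved. The combination table instead offers a dose-finding action. Below the RP2D the row is right, because it takes a lead-in that started one level down up to the dose under test. At the RP2D it sends a good result upward, and no written sentence stops it there.

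Followed literally, a clean first cohort at the RP2D leads to a dose change instead of enrolment to 6 and a tolerability decision. In the least favourable setting, the next cohort would receive ASP0739 above its single-agent MTD with pembrolizumab added, although Protocol 4.2 warns that the combination may increase the frequency or severity of toxicities.

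**Working it through.** **1. The plan's own figures.** Inputs from Protocol 4.1: target DLT rate 0.30, interval (0.236, 0.359). Assumed, because not stated: the usual BOIN defaults φ₁ = 0.6 × 0.30 = 0.18 and φ₂ = 1.4 × 0.30 = 0.42, and stopping when P(rate > 0.30) exceeds 0.95 under a Beta(1,1) prior.

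- λₑ = ln[(1 − 0.18)/(1 − 0.30)] / ln[0.30 × 0.82/(0.18 × 0.70)] = 0.2365
- λ_d = ln[(1 − 0.30)/(1 − 0.42)] / ln[0.42 × 0.70/(0.30 × 0.58)] = 0.3585

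Both match the stated interval, and every cell for n = 3 to 8 reproduces. The thresholds are correct; the difficulty is the action attached to them.

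**2. Where Escalate points once the lead-in is at the RP2D.** Table 8 lists 1×10⁷ and 1×10⁸; the text of 4.1 also allows a reduction to 1×10⁶.

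| Phase 1 result | Escalate points to | Consequence |
|---|---|---|
| RP2D = MTD = 1×10⁷ | 1×10⁸ | above the single-agent MTD |
| RP2D = MTD = 1×10⁶ | 1×10⁷ | above the single-agent MTD; the start one level lower also has no defined dose |
| RP2D = 1×10⁷, MTD = 1×10⁸ | 1×10⁸ | above the dose under test, not above the MTD |
| RP2D = 1×10⁸ | no higher dose | labelling gap only |

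**3. How often an Escalate cell is reached at the RP2D.** The documents give no DLT rate for the combination, so q = 0.10, 0.20, 0.30 are assumed. The second cohort is taken to be the same size as the first.

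- 3+3: P(0/3) + P(1/3)P(0/3) = 0.729 × 1.243, 0.512 × 1.384, 0.343 × 1.441 = 0.906, 0.709, 0.494
- 4+4: P(0/4) + P(1/4)P(0/4) = 0.656 × 1.292, 0.410 × 1.410, 0.240 × 1.412 = 0.847, 0.577, 0.339

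**4. The path above the MTD when RP2D = MTD = 1×10⁷.** The lead-in starts at 1×10⁶; two clean cohorts of 3 then point participants 7 to 9 to 1×10⁸. With assumed rates at 1×10⁶ and 1×10⁷ of:

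- 5% and 10%: 0.95³ × 0.90³ = 0.625
- 10% and 20%: 0.90³ × 0.80³ = 0.373
- 20% and 30%: 0.80³ × 0.70³ = 0.176

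These are conditional on this phase 1 result and on literal use of the table. The path uses 3 + 3 + 3 = 9 participants and leaves no level with 6.

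**5. What a second cohort at the RP2D would add after a clean first one.** From a clean start, the table reads de-escalate or stop only at 3 or more DLTs in total.

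- 3+3: P(0/3)P(3/3) = 0.0007, 0.0041, 0.0093, or 0.07%, 0.4%, 0.9%
- 4+4: P(0/4)P(≥3/4) = 0.0024, 0.0111, 0.0201, or 0.2%, 1.1%, 2.0%

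**6. With the footnote proposed below.** Tolerable means at most 1 DLT in 6 (3+3) or in 8 (4+4). Referral means 2 in total, with 0 or 1 in the first cohort. Two or more DLTs in the first cohort still de-escalate or stop.

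| q | 3+3 tolerable | 3+3 referred | 4+4 tolerable | 4+4 referred |
|---|---|---|---|---|
| 0.10 | 0.886 | 0.079 | 0.813 | 0.117 |
| 0.20 | 0.655 | 0.197 | 0.503 | 0.231 |
| 0.30 | 0.420 | 0.259 | 0.255 | 0.233 |

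**The case against.** The surrounding text points to the RP2D as the natural ceiling. The lead-in evaluates the RP2D, the only dose changes its text describes are a lower start and a step down, and a dose above the MTD could not go forward to expansion. Protocol 2.3.2 says the DESC is guided by BOIN, and 10.1.5.2 has it weigh all safety findings, which would include the single-agent data that set the MTD. Section 4.1 also foresees a combination RP2D, so a step from 1×10⁷ to an MTD of 1×10⁸ might be intended. Early data do not favour a low MTD: Protocol 2.3.1.1 reports no DLTs in 4 participants at 1×10⁷. All of this stands and makes actual overdosing unlikely. None of it writes the missing ceiling or supplies a tolerable outcome.

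Three stronger readings are not supported.

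- A reader might infer that Escalate at 0/3 or 0/4 contradicts the minimum of 6. That minimum applies to the dose used to determine the RP2D, not to every level visited, and phase 1 pairs the same table with the same sentence. It is a tension, not a contradiction.
- A reader might take 91%, 71% and 49% as overdose probabilities. They are mostly the chance of a reassuring first cohort.
- A reader might treat every second cohort with 2 DLTs as showing the first decision was premature. But 0/3 then 2/3 is 2/6, and 0/4 then 2/4 is 2/8; the table reads both as Stay. The relevant figures are those in step 5, at most 2.0%.

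**Conclusion.** The point holds as a fault in the decision rule. The BOIN counts are right, but at the RP2D the best results carry an action that does not answer the lead-in's question. In two of the four phase 1 results tabulated, that action points above the single-agent MTD. An Escalate cell is the usual outcome if the combination is well tolerated: 91% (3+3) or 85% (4+4) at an assumed DLT rate of 10%.

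The practical weight is modest. The path above the MTD needs a single-agent MTD below 1×10⁸, a probability the documents do not allow one to estimate, and it needs the DESC to follow the table literally. The SAP Introduction records that no combination treatment took place, so no participant or result was affected. The correction matters for the design text and for any reuse of it. All probabilities rest on assumed DLT rates and equal cohort sizes.

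**What to change.** Keep the Escalate row for a lead-in below the RP2D and add one footnote to the combination table:

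> ASP0739 will not be escalated above the single-agent RP2D, and never above the single-agent MTD, in the lead-in. At the RP2D, a result in this row means continue at that dose to at least 6 DLT-evaluable participants; 1 or fewer DLTs in 6 to 8 means the combination is tolerable; 2 DLTs in 6 to 8 at the end of the lead-in is referred to the DESC.

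No threshold changes, and the approach mirrors the Japanese lead-in and its TEM. There are two small costs. Raising the combination dose from an RP2D of 1×10⁷ to an MTD of 1×10⁸ would need an amendment. A lead-in that starts below the RP2D should use a first cohort of 3 (3 + 6 = 9, within the plan), because a cohort of 4 needs at least 4 + 6 = 10 against a planned 6 to 9.
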